**NCT03377816: The Role of Emotional Processing in Improving the Quality of Life of
Breast Cancer Patients (REPAT)**

Statistical Analysis Plan- September 14th, 2017

The following statistical analysis plan was written in September of 2017 as part of the grant proposal for the REPAT study and was incorporated into the study protocol and guided the design of the actual study.

C.5 Statistical Methods:

C.5.1 Sample Size: A power analysis was conducted via Monte Carlo simulation in Mplus showed that a sample size of 240 (120 per condition), provides: (1) >90% power to detect a moderate effect size (Cohen's $d = 0.50$) of treatment on mechanisms, (2) >90% power to detect a moderate association ($r = 0.30$) between mechanisms and symptoms, and (3) >90% power to detect an indirect effect from treatment to symptoms via mechanisms. The sample size will also provide >80% power to detect a moderate effect size for the Condition by Ethno-Cultural group interaction.

C.5.2 Data Analysis: Prior to testing hypotheses, we will produce a thorough descriptive profile of the sample and examine the distributions of key variables involved in the hypotheses. We will also examine levels of nonresponse and **missing data**. Prior experience indicates attrition will be low; although, some missing data are expected due to missed assessments and dropout. Data will be analyzed using full information maximum likelihood to address missing data, supplemented with pattern-mixture modeling for non-random missingness. The first part of Hypothesis 1: women in the AT group experience greater increases in emotion processing, HRV, and regulatory cytokine levels and greater decreases in pro-inflammatory cytokines than women randomized to the Mandala condition will be tested using linear mixed models¹²⁹. Models will include a Time x Condition interaction to test whether the change over time in emotion processing and cholinergic anti-inflammatory processes is significantly different between treatment groups.

A significant interaction will be followed up by simple slope tests to characterize the degree of change separately in the AT and Mandala conditions.

The second part of Hypothesis 1: emotion processing and cholinergic anti-inflammatory processes mediate the effects of AT on symptoms (depression, pain, fatigue) will be tested using path analysis.

Specifically, models will be tested where condition (AT versus Mandala) predicts the change in emotion processing or physiological correlates (path a) and the change in emotion processing or physiological correlates predicts the change in symptoms (path b). Mediation will be tested by calculating the indirect effect as the product of coefficients (path a x path b) and utilizing bootstrapping to calculate 95% confidence intervals and statistical significance¹³⁰.

Hypothesis 2: changes in emotion processing and cholinergic anti-inflammatory processes will be correlated and have unique effects will be tested by expanding the path analyses from Hypothesis 1 to simultaneously include all proposed mediators on each symptom outcome. Indirect effects with bootstrapped confidence intervals will be calculated as before. The change in mediators will be allowed to freely correlate to examine their relations.

[figure not shown]

Figure 3: Model hypotheses 1 & 2

The Exploratory Hypothesis posits a sequential mediation model from treatment (AT versus Mandala) to emotion processing (path a) to cholinergic anti-inflammatory processes (path b) and finally to symptoms (path c). To establish temporal precedence, change in emotion processing from baseline to intervention midpoint and change in cholinergic anti-inflammatory processes from intervention midpoint to completion, and change in symptoms from baseline to intervention completion will be used. Indirect effects will be calculated as the product of three coefficients (path a x path b x path c) capturing the hypothesized sequentially mediated effect. Bootstrapped confidence intervals and significance tests will be calculated. To test the reverse ordering, the same process will be used exchanging the time points and order of emotion processing and cholinergic anti-inflammatory processes.

[figure not shown]

Figure 4: Model Hypothesis 3

Hypothesis 3: the effect of AT versus SHAM on emotional processing will be stronger in women from an ethno-cultural minority group will be tested by expanding the linear mixed models from Hypothesis 1 by including measures of traditional values as a covariate and a Time x Condition x Ethno-Cultural Group (Jewish vs Arab) interaction to test whether ethno-cultural group moderates the Time x Condition interaction from Hypothesis 1. If the three-way interaction is significant, simple slopes will be calculated and graphed to characterize the change in emotion processing by treatment condition and ethno-cultural group.

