3. STUDY DESIGN

We will accomplish the aims by a randomized controlled trial of 240 Jewish and Arab women (>18 years) who have been diagnosed with BC and have completed chemotherapy, recruited in Israel and randomized to undergo an 8-week (1.5 hours per week) program of group Art Therapy compared to women who will be designated to an 8-week sham Art Therapy group. We chose this design to be able to isolate and examine emotional processing and the effect of enhancing emotional processing on HRV and inflammatory cytokines and examine how these may mediate the effect of art therapy on depressive symptoms, pain and fatigue.

The primary outcomes are emotion processing, comprised of emotion awareness, expression and acceptance and the cholinergic anti-inflammatory pathway, comprised of resting HRV and inflammatory (pro and regulatory) cytokines. The secondary outcome measures are depression, pain and fatigue.

The study will take place at the cancer centers of 3 study sites: Rabin Medical Center, Rambam Medical Center and Ziv Medical Center, the enrollment period will vary until each cohort is collected and is expected to be approximately a month or a month and a half.

The interventions will be administered by an experienced Art Therapist who will be trained in this specific protocol by the PI [name] who is an Art Therapy [name] intervention is designed to follow the Bodymind model of AT⁶². Each session will start with a ten-minute rapport building and touching base and continue with 50 minutes of art making in a calm and supportive environment. Art materials are on the table and after the art therapist provides a brief explanation of the use of the materials; participants are encouraged to explore and experience as they wish. The art therapist is present to guide and assist. Participants are encouraged to minimize conversation; instrumental music is played to encourage introspective experiences. The session ends with 30 minutes of processing and discussion in which each participant shares and briefly presents their work and group participants can respond and or provide support.

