5. STUDY INTERVENTIONS

5.1 Interventions, Administration, and Duration

Both interventions will be administered in a group format by a trained individual. Each session will be 1.5 hours (intervention) and an hour (comparison) once a week for 8 weeks. There is a risk of participants feeling distress due to the exposure to emotional content either discussed in the group or that arises in the art therapy intervention group. The psychosocial team at each study site will be prepared to meet with any participant who requests so. Interventionists will be trained to identify and refer distressed participants to the psychosocial team.

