Session 7: Body image: In this module participants will create art using body outline templates as a framework for art making. The goal of this session is to increase introceptive awareness and assist in processing emotional content from implicit experience to explicit expression. Distress tolerance.

Session 8: Summary: This session will be a summary of all that has been experienced and clients will be provided with a letter that summarizes their progress. Each client will receive a package of oil pastels and blank journal for the encouragement of their continued process at home. The goal of this session is to review achievements and encourage incorporating what was learned in day to day life after the intervention is over.

The comparison group is designed to control for the impact of the aspect of the group experience that are not explicitly focused on emotional processing, ie, the time with art materials and focused attention aspects that occur during an Artmaking session. These sessions will not have a rapport building component and will include 40 minutes of coloring pre-fabricated shapes (Mandalas- see figure 3) in a calm environment and 20 minutes of self-care instruction. Coloring Mandala's has been demonstrated to reduce anxiety⁶⁸⁻⁷⁰. Participants are encouraged to minimize conversation; instrumental music is played to encourage introspective experiences. Due to our concerns that participants will become bored after more than 40 minutes of coloring we will not be equally comparing the amount of time that participants are together in the group format.

Figure 3: Mandala example

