8.2 Sample Size and Randomization

A power analysis was conducted via Monte Carlo simulation in Mplus showed that a sample size of 240 (120 per condition), provides: (1) >90% power to detect a moderate effect size (Cohen's $d = 0.50$) of treatment on mechanisms, (2) >90% power to detect a moderate association ($r = 0.30$) between mechanisms and symptoms, and (3) >90% power to detect an indirect effect from treatment to symptoms via mechanisms. The sample size will also provide >80% power to detect a moderate effect size for the Condition by Ethno-Cultural group interaction.

Consented participants will be randomized into the Art Therapy or Sham condition using block randomization stratified by site, ethnicity and traditionalism to ensure equal sample sizes between groups over time in each site and in each ethnicity. Permutations of group assignment will be generated in random blocks of 4, 6, and 8 so that staff cannot guess the condition of the final participant as the block size varies. Condition assignment will be stored in sealed, numbered envelopes to be opened consecutively as subjects enroll and the envelopes will designate individuals to the intervention through use of a random numbers table. PI [name] will provide the PhD students with the randomized lists (60 each cohort), who will schedule sessions and make weekly calls to encourage attendance, therefore both will be un-blinded to study assignment. The Research Nurse will collect and enter data, collect bio specimens and manage the database, and thus will be un-blinded after randomization. The research assistant (RA) will remain blinded throughout the study, and will receive lists of participants to call, without knowing which group they are assigned to. Participants will be told they are participating in an "art making" study where they will be assigned to an art making group. Participants will not be told which is expected to be superior.

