8.3 Treatment Assignment Procedures

Consented participants for each cohort will be randomized (PI- [name]) The University statistician will generate numbered envelopes to be opened consecutively as subjects enroll and the envelopes will designate individuals to the intervention through use of a random numbers table. PI [name] will provide the PhD students with the randomized lists (60 each cohort), who will schedule sessions and make weekly calls to encourage attendance and conduct the intervention and thus will be unblinded. The Research Nurse will collect and enter data, collect bio specimens and manage the database, but will remain blinded after randomization. The research assistant will remain blinded throughout the study, and will receive lists of participants

to call, without knowing which group they are assigned to. Participants will be told they are participating in an “art making” study where they will be assigned to either the intervention group or the sham intervention (Mandala) group. Participants will not be told which is expected to be superior.

Table 4: Roles in the study

Title	Blinded to group assignment	Roles	Rambam	Ziv	Beilinson
Research nurse (employee of each hospital).	Yes	Recruit and obtain verbal consent, collect blood.	1	1	1
Research coordinator (employee of each hospital).	Yes	Assist MD in recruiting patients, collect data (questionnaires and HRV), transfer blood to the lab for processing (separation to serum, divide in 4 aliquots and cryopreservation -80)	1	1	1
Art Therapist	No	Conduct intervention groups (8.5 weeks)- Art Therapy and SHAM in Hebrew or Arabic	2	2	2
PhD student	No	Conduct groups, supervise interventionists, assist in fidelity assurance, assist in data analysis.	3		
Laboratory worker	Yes	Conduct inflammatory cytokines analysis.	1		
Research coordinator	Yes	Coordinate between study site, transport frozen serum to lab, input data	1		

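### Both arms are treated in therapy groups, but no model, bootstrap or power text accounts for the group; the Hypothesis 1 test may exceed its nominal 5% error, by an amount that depends on unstated group size and correlation

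*SAP*

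**What the plan says.** **Allocation is individual.** Protocol 8.2: "Consented participants will be randomized into the Art Therapy or Sham condition using block randomization stratified by site, ethnicity and traditionalism", with the aim "to ensure equal sample sizes between groups over time in each site and in each ethnicity".

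**Delivery is in groups, in both arms.** Protocol 5.1: "Both interventions will be administered in a group format by a trained individual". In art therapy (AT), Protocol 3 adds: "The session ends with 30 minutes of processing and discussion in which each participant shares and briefly presents their work", and other members may respond or give support. The comparison sessions are described differently in Protocol 5.2: "These sessions will not have a rapport building component and will include 40 minutes of coloring pre-fabricated shapes", followed by self-care instruction and with conversation kept to a minimum. Table 4 in Protocol 8.3 gives the art therapists' task as "Conduct intervention groups (8.5 weeks)- Art Therapy and SHAM in Hebrew or Arabic".

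**Analysis.** SAP C.5.2 on Hypothesis 1: "Models will include a Time x Condition interaction to test whether the change over time in emotion processing and cholinergic anti-inflammatory processes" differs by treatment. It lists no random effects and no stratification factors. The path models rest on bootstrap intervals with no resampling unit named. Hypothesis 3 adds traditional values and ethno-cultural group. Site appears in no model.

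**Power.** SAP C.5.1 and Protocol 8.2 give 240 women, d = 0.50, r = 0.30 and the resulting power. They give no group size, ICC or design effect.

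**The concern.** Women who share a leader and a room, and in AT respond to each other's work, may change together. If so, 120 women in an arm carry less information than 120 independent women. The shared effect arises after baseline, so it sits in the change that Time x Condition tests. A participant intercept removes stable differences between women and leaves this effect untouched. The strata cannot stand in for the therapy group either, because each group belongs to one arm.

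At stake are the tests on the primary outcomes (emotion processing, HRV, cytokines) and, through path a, the mediation claims. A false signal on path a would be read as evidence of mechanism, which is the purpose of this trial.

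**Working it through.** **Inputs from the documents.** 240 women, 120 per arm, d = 0.50 (SAP C.5.1); 60 women per cohort (Protocol 8.2); 3 sites (Protocol 3); groups in Hebrew or Arabic (Protocol 8.3).

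**Assumptions.** Two-sided 5% level. Group size m: 60 / (3 sites x 2 arms) = 10, or 60 / (3 x 2 x 2 languages) = 5. ICC of change: 0.01 to 0.10. Share s of change variance carried by the strata: 5% to 10%. A participant intercept and no other random effect. The ICC may differ between questionnaires, HRV and cytokines.

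**Step 1: the plan's own figure.** With independent women, the noncentral t with 238 df gives 97.1% power for d = 0.50. This agrees with the stated bound of more than 90%.

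**Step 2: error of the unadjusted test.** Two effects oppose each other. Within-group correlation makes the model's standard error too small. Balanced strata left out of the model make it too large. With change variance set to 1, the ratio of true to assumed variance of the arm difference is

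D = 1 - s + (m - 1) x ICC,

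with (m - 1) x ICC halved if only AT clusters. True error = 2 x [1 - Phi(1.96 / sqrt(D))].

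Example: m = 10, both arms, ICC 0.05, s = 0.05 gives D = 1 - 0.05 + 9 x 0.05 = 1.40 and an error of 9.8%. Across s = 10% to 5%:

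| Groups | Clustering | ICC 0.01 | ICC 0.05 | ICC 0.10 |
|---|---|---|---|---|
| 5 | AT only | 4.1-4.7% | 5.0-5.6% | 6.2-6.8% |
| 5 | both arms | 4.3-4.9% | 6.2-6.8% | 8.6-9.2% |
| 10 | AT only | 4.4-4.9% | 6.5-7.1% | 9.2-9.8% |
| 10 | both arms | 4.9-5.5% | 9.2-9.8% | 14.4-15.0% |

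A simulation (40,000 runs per cell; change-score test and three-visit random-intercept model) gave, at ICC 0.05, 5.0-5.9%, 6.1-7.3%, 6.6-7.4% and 9.1-10.3% in the same row order.

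**Step 3: break-even.** D = 1 when ICC = s / (m - 1), or twice that for AT only.
- Lowest: groups of 10, both arms, s = 5%: 0.05 / 9 = 0.006.
- Highest: groups of 5, AT only, s = 10%: 2 x 0.10 / 4 = 0.05.

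**Step 4: Hypothesis 3.** The direction depends on language. With separate-language groups of 5, both arms clustered and s = 0, the three-way test has an error of 7.4% at ICC 0.05. With mixed-language groups of 10 it is slightly conservative (4.5%).

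**Step 5: indirect effects.** With a = 0 and b = 0.3, a percentile bootstrap that ignores groups rejects at 5.4% (groups of 5) or 5.7% (groups of 10) when the ICC is 0. At ICC 0.05 the figures are 7.8% and 10.4%, for both arms clustered and s = 0. A smaller check at ICC 0.05 with only AT clustered and s = 5% to 10% (1,500 runs per cell, simulation error about 0.6 points) gave about 5.5-6.3% and 7.1%.

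**Step 6: power with groups respected.** The variance is multiplied by 1 + (m - 1) x ICC and df = number of groups - 2: 240/5 - 2 = 46, or 240/10 - 2 = 22. This takes both arms clustered and no strata effect.

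| Groups | ICC 0 | ICC 0.05 | ICC 0.10 | Below 90% above ICC |
|---|---|---|---|---|
| 5 | 96.6% | 93.3% | 89.3% | 0.092 |
| 10 | 95.9% | 86.7% | 76.6% | 0.034 |

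**The case against.** **The milder cases fit the documents better.** Peer discussion is described for AT only, and the comparison sessions are low in interaction. The references to Hebrew and Arabic groups in Protocol 8.3 and 9.3.3 point to separate-language groups, hence groups of about 5. In that case (AT only, groups of 5) the error at ICC 0.05 is 5% to 6%. A reader might infer from the last row of the error table that the test runs at about twice its nominal level. The documents do not support that as the expected case. They do not exclude it either, since a shared leader and setting could also cluster the comparison arm.

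**The offset may be larger than assumed.** If the same therapists lead both arms equally, a leader effect acts like another omitted stratum and adds to s. At s = 15% to 20%, break-even for AT-only groups of 5 rises to 2 x 0.15 / 4 = 0.075 and 2 x 0.20 / 4 = 0.10. So it would also be wrong to infer that any small correlation inflates the error.

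**The SAP's silence is weak evidence.** It names linear mixed models without naming even a participant effect, so a group effect might be fitted in practice. That is fair, but a plan should settle it beforehand. Protocol 5.4 has the interventionist record attendance, so group membership may be recoverable, although no section says that it is kept as an analysis variable.

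**Part of the bootstrap excess is not clustering.** This stands: the percentile bootstrap already exceeds 5% slightly at ICC 0.

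**Conclusion.** The omission is real: group delivery in both arms, and no therapy group in any model, bootstrap or power statement. Its effect is conditional. At ICC 0.05 with s = 5% to 10%, the nominal 5% Hypothesis 1 test has a true error of about 5-6% (groups of 5, AT only), 6-7% (groups of 5, both arms), 6.5-7.5% (groups of 10, AT only) or 9-10% (groups of 10, both arms). At ICC 0.01 there is little or no excess. Indirect effects inherit the excess through path a when a = 0 and b is not 0.

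A reader might conclude that the power claim is false. It is not shown to be. It holds under independence and for part of the ICC range, and it remains unsupported until group size and an ICC range are stated. Confidence is high for the omission. The size rests on assumed group size, ICC, strata share and random-effects structure. This should be fixed before analysis.

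**What to change.** 1. **SAP C.5.2, Hypotheses 1 and 3.** Record each woman's therapy group. Add a therapy-group random effect on the post-baseline visits, with variance allowed to differ by arm and a stated simplification if the model does not converge. Add site, ethnicity and traditionalism with their time interactions. Test with Satterthwaite or Kenward-Roger degrees of freedom. In simulation, a simpler balanced form of this test (site x ethnicity strata, no dropout) held 4.8% to 5.3%; the full model was not simulated.
2. **SAP C.5.2, path models.** Use inference that accounts for therapy group. Beside each Hypothesis 1 and 2 indirect effect, report the group-adjusted test of path a from item 1, so that an indirect effect whose path a is unsupported is read with caution. Whole-group resampling alone is not enough: with this few groups it left about 6% to 8% error. Joint rejection should not become a required rule. It would replace the SAP's mediation criterion, cut indirect-effect power for groups of 10 from 94% to 87% (ICC 0.05) or from 90% to 75% (ICC 0.10), and it is undefined for the sequential model.
3. **SAP C.5.1 and Protocol 8.2.** State the planned number and size of groups, and restate power for the treatment-on-mechanism and indirect-effect claims over an ICC range such as 0.01 to 0.10.

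**Cost.** One recorded variable and SAP wording; no additional patients. If there is no clustering, the group-level test with strata loses about 0.5 points of power (97.1% to 96.6%, groups of 5) to 1.4 points (97.1% to 95.7%, groups of 10). The stated power may become less favourable.

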The comparison group will meet for a half an hour. The interventionist will encourage the participants to color prefabricated shapes for 30 minutes. The same art materials as in the intervention group will be on the table as will the same instrumental music. We will not be controlling for the whole 90 minutes of the intervention group as are concerned that comparison group participants will become bored and this will defeat the purpose of the comparison group. The detailed role of the interventionist is described in section 5.2, and it is tailored to ensure optimal opportunities for participants to engage in emotional processing in a supportive environment.

The interventionists of both groups will keep scores that will be rated by the PI against the treatment manual to ensure fidelity (see Table 2).

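### If the mediation models use computed change scores, a woman who misses the whole later visit is lost with her baseline, and path a can be biased when dropout differs by arm

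*SAP*

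**What the plan says.** The second part of Hypothesis 1 (SAP C.5.2) is tested by path analysis. In these models "condition (AT versus Mandala) predicts the change in emotion processing or physiological correlates (path a"). For path b, symptom change is regressed on mediator change. The indirect effect is the product a x b, with bootstrapped intervals. Hypothesis 2 is tested by "expanding the path analyses from Hypothesis 1 to simultaneously include all proposed mediators on each symptom outcome". No baseline score appears in the description as a covariate, an auxiliary variable or a separate model variable. The text does not say whether change is a computed difference or a latent change built from two scores.

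The missing-data statement is general: "Data will be analyzed using full information maximum likelihood to address missing data, supplemented with pattern-mixture modeling for non-random missingness". It does not say which models the pattern-mixture supplement covers.

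The first part of Hypothesis 1, the effect of treatment on the mechanisms, uses a linear mixed model: "Models will include a Time x Condition interaction to test whether the change over time in emotion processing" and the physiological processes differs by arm.

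The protocol (Sample Size and Population) expects 15% attrition. SAP C.5.2 expects it to be low.

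**The concern.** Maximum likelihood recovers information only from variables that are in the model. If the model contains condition, the change in the mediator and the change in symptoms, a woman who misses the whole later visit has both changes missing. She contributes nothing to path a or path b, although her baseline was collected. The missing-at-random assumption then conditions on arm alone.

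If the women who leave one arm differ at baseline from those who leave the other, the completers' baselines differ by arm. Regression to the mean turns that into an arm difference in change that treatment did not cause. It enters path a and is carried into a x b, which is the quantity behind the trial's mechanistic aim. The mixed model does not supply the a in a x b, so it does not protect the mediation result.

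**Working it through.** **Inputs from the documents.** 240 women, 120 per condition, and d = 0.50 for treatment on mechanisms with power above 90% (SAP C.5.1); 15% attrition (protocol, Sample Size and Population).

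**Assumptions, not in the documents.** Two-sided alpha 0.05; pre-post correlation r from 0.3 to 0.7; dropout logistic in the mediator's own baseline, with slopes in log-odds per SD; 15% applied to the 240 randomised, leaving 0.85 x 120 = 102 per arm.

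**1. The plan's own figure.** Power = Φ(0.5/√(2/120) − 1.96) = Φ(3.87 − 1.96) = 97.2%. With 102 per arm it is Φ(3.57 − 1.96) = 94.6%. Both agree with the stated bound, and nothing below alters it.

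**2. Does maximum likelihood on change scores use the baseline?** One simulated data set was fitted with condition → change in mediator → change in symptom.
- Whole later visit missed: path a is 0.3967 by full information maximum likelihood and 0.3967 in complete cases (216 of 240 women). The baseline is not used.
- Only one of the two changes missing for some women: maximum likelihood uses 214 women against 162 complete cases, and path a is 0.389 against 0.347. Here it is not a complete-case analysis.

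**3. Size of the bias.** With equal variances, a completer whose baseline is x SD from the mean has expected change −(1 − r)x plus the treatment effect. So

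bias in path a = −(1 − r) x (completers' mean baseline in AT − completers' mean baseline in Mandala).

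Simulated path a from observed changes (4,000 runs per scenario, true value 0.50, 15% dropout per arm):

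| Dropout and baseline mediator | r = 0.3 | r = 0.5 | r = 0.7 |
|---|---|---|---|
| Unrelated | 0.50 | 0.50 | 0.50 |
| Same slope in both arms | 0.50 | 0.50 | 0.50 |
| Slope −1 in AT only | 0.41 | 0.43 | 0.46 |
| Slope −1 in AT, +1 in Mandala | 0.31 | 0.37 | 0.42 |

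In the last row, 95% interval coverage is 79%, 84% and 88%. The table fits the formula. At r = 0.5 with the slope in AT only, the bias of 0.500 − 0.434 = 0.066 implies a completer imbalance of 0.066/0.5 = 0.13 SD. The same imbalance predicts 0.50 − 0.7 x 0.13 = 0.41 at r = 0.3 and 0.50 − 0.3 x 0.13 = 0.46 at r = 0.7.

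Other scenarios at r = 0.5:
- Opposite slopes with the signs swapped: 0.63.
- Opposite slopes: 0.46 at 5% dropout, 0.25 at 30%.
- Same slope but unequal dropout (25% AT, 5% Mandala): 0.42.

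With baseline and follow-up both in the likelihood, or baseline as a covariate, the estimate lies between 0.497 and 0.504 in every scenario.

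**4. False positives with no true effect** (r = 0.5, 15% dropout, opposite slopes). The variance of change is 2(1 − 0.5) = 1, so the standard error is √(2/102) = 0.140. A bias of 0.131 is 0.131/0.140 = 0.94 standard errors, and the rejection rate is Φ(−1.02) + Φ(−2.90) = 0.154 + 0.002, about 16%. Simulation gives 15% to 16%. With slopes of 0.5 the simulated bias is 0.07 to 0.08 SD and the type I error about 8% to 9%. With baseline in the model, type I error is about 5%.

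**5. Dropout driven by distress instead.** If dropout follows baseline distress, and distress correlates 0.3 with the mediator, the bias with opposite slopes of 1.0 is about 0.3 x 0.13 = 0.04 SD (simulated type I error 6.0%). At a correlation of 0.5 it is about 0.06 SD (7.8%).

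**6. Precision under random dropout.** Residual variance is 2(1 − r) for a change score and 1 − r² with baseline adjustment. At r = 0.5 the ratio of standard errors is √(0.75/1.00) = 0.866, a reduction of about 13%.

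**The case against.** The strongest reply is that the SAP never says the change is precomputed. A latent-change path model fits its words, agrees with its stated missing-data method and is free of this bias. The path diagram for Hypotheses 1 and 2 is not legible in the text available and might show baseline variables. This stands, so the point is conditional and no definite error is shown.

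A reader might infer that the mediation models simply become complete-case analyses. They do so only for a wholly missed visit. Questionnaires, ECG and blood are separate measurements (protocol 6.2), so partial missingness is plausible, and maximum likelihood keeps those women.

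A reader might also infer that the protocol foresees arm-specific dropout. It does not. Protocol 5.1 says "There is a risk of participants feeling distress due to the exposure to emotional content", but it covers both interventions, provides for referral and does not mention leaving. Protocol section 3, being "concerned that comparison group participants will become bored", gives this as the reason for a shorter comparison session. Neither passage ties leaving to a baseline score. They make differing reasons for dropout conceivable and no more.

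Nor does the bias necessarily flatter art therapy. If more distressed women left art therapy and less distressed women left the comparison group, and the mediators are better when distress is lower, art therapy would look worse.

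Two safeguards deserve credit. The Hypothesis 1 mixed model keeps baseline-only women if baseline is a modelled time point. The pattern-mixture supplement exists, but it is aimed at non-random missingness and is not tied to the mediation models. Dropout explained by an observed baseline is missing at random once that baseline is in the model.

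**Conclusion.** The point holds as a conditional weakness with a cheap remedy. On the natural reading of C.5.2, the path models discard the baseline of any woman who misses the whole later visit. Bias in path a and a x b then requires dropout related to the mediator's baseline differently by arm, or related to it at unequal dropout rates.

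With r = 0.5, 15% dropout and slopes of 1.0, all assumed, the bias is about 0.07 SD (one arm only) to 0.13 SD (opposite slopes). It is about 0.05 SD or less at 5% dropout, smaller again if dropout follows distress that is only loosely correlated with the mediator, and zero if dropout is unrelated to baseline or related to it equally in both arms at equal rates. Its direction is not known in advance.

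The stated power is unaffected. The documents do not support saying that the mediation results will be biased. The change is still worth making, because it removes a possible bias and gains precision even if dropout is random.

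**What to change.** State in SAP C.5.2 that each path model enters the baseline and follow-up mediator and symptom scores as separate variables under full information maximum likelihood, for every randomised woman, and that precomputed differences are not used. Either follow-up adjusted for baseline or a latent-change model will do. The 13% gain in precision comes with baseline adjustment, or with a latent-change model that has no path from condition to baseline. Also state which models the pattern-mixture analysis covers.

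It is not necessary to put all three assessments of every variable into one model. Each path model needs only the baseline and the follow-up visit that it concerns.

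No new data are needed, since the baselines are already collected. The cost is SAP wording and somewhat larger models. It is most noticeable for Hypothesis 2, where the emotion-processing scales, HRV and seven cytokines each gain a baseline variable at N = 240.
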